Patients will return to clinic at least weekly for assessments (until the last week of protocol therapy). Refer to the Study Calendar, Appendix 18, for evaluations to be completed during each clinic visit. Each clinic visit will include: assessment of vital signs (blood pressure, pulse and temperature). The following will be performed only on a weekly basis (usually on the first visit of each week) unless clinically significant values were obtained at the previous visit: physical exam; assessment of the ECOG/ Karnofsky Performance Status; assessment of concomitant medications; assessment of adverse events; completion of a serum chemistry panel; completion of a CBC with differential. At the beginning of every cycle a urinalysis panel will be completed. A 12-lead ECG and echocardiogram will be performed at baseline. Additional ECGs/ echocardiograms should be obtained on any patient who demonstrates signs or symptoms of myocardial degeneration. Additionally a 12-lead ECG will be performed 2 hours and 24 hours after the first infusion of SGT-53. A 12-lead ECG will be performed weekly (2 hours postinfusion) during the first 2 weeks of cycle 1, and at the End Of Treatment (EOT) visit. If these patients receive additional rounds of SGT-53/Temozolomide a 12-lead ECG will only be performed as necessary and at the EOT visit.

The first two subjects enrolled in this trial under the current protocol will be monitored for PT/PTT, D-dimer and LDH at baseline/screening; in cycle 1 ~20 hours after the first infusion (during the 23 observation period), and weekly during cycle 1, and once in two weeks during cycles 2 and 3 and at the exit visit. If these patients receive additional rounds of SGT-53/Temozolomide PT/PTT, D-dimer and LDH will be monitored once in two weeks during cycle 1 and monthly in cycle 2 and beyond.

Subsequent subjects will be monitored for PT/PTT, D-dimer and LDH at:

- (i) baseline/screening;
- (ii) in cycle 1 (a) ~20 hours after the first infusion (during the 23 observation period)
- (iii) at the exit visit.

Patients who are responding to treatment (at least stable disease by RANO) may receive three additional cycle of SGT-53/temozolomide therapy at investigator's discretion. Alternatively, they may continue on Temozolomide alone at investigator's discretion.

10.2.4. End of Treatment Evaluations (Day 85, at the end of Cycle 6 if the patient received cycles 4-6, or for premature withdrawal/study drug discontinuation)

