Once a patient has completed study treatment, including premature withdrawal/study drug discontinuation, the patient should complete an End of Treatment Visit. During this visit the following assessments will be completed:

- Radiographic tumor measurement
- Complete medical history
- Physical examination (all body systems)
- Karnofsky Performance Status
- Vital signs (temperature, blood pressure, pulse rate, and respiratory rate)
- Concomitant medication assessment
- Serum chemistry including: sodium, chloride, carbon dioxide, potassium, calcium, phosphorous, magnesium, BUN, creatinine, blood sugar (random), albumin, alkaline phosphatase, alanine aminotransferase, aspartate aminotransferase, bilirubin (total, direct), and total protein.
- CBC with differential and platelet counts
- 12-lead electrocardiogram
- Limited Echocardiogram, only if needed
- Urinalysis
- Assessment of adverse events

10.3. **Follow-up**

If the patient was removed from the Study for toxicity, the patient should be followed with weekly clinic visit and laboratory studies as appropriate, at clinical trial site or the patient's local MD, until the AE has resolved to baseline or is documented as irreversible.

All patients who received treatment with SGT-53 must be followed-up for 30 days after discontinuation of study drug. The 30-day follow-up visit should include a physical examination, vital signs, concomitant medications and assessment of AEs/SAEs and Urine analysis. Blood samples will be taken for: Hematology (CBC with differential, platelet count), Chemistries (BUN, Cr, Na⁺, K⁺, CO₂, Cl, Mg⁺⁺, Ca⁺⁺, phosphorus, albumin, alkaline phosphatase, ALT, AST, total bilirubin, total protein, glucose), PT/PTT, D-dimer, LDH.

Patients who permanently discontinue study drug(s) for reasons other than complete response, progression, or death should also have visits approximately every 2 months for the first year that should include a MRI, physical examination, vital signs, and recording of concomitant medications for glioblastoma.

Patients who are withdrawn from study treatment due to a complete response will have the 30-day follow-up visit as described above and in Sections 5 and 9.4.1. Further follow-up visits every 2 months will include only a physical/neurological exam, concomitant medications, vital signs and an MRI.

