11.5. Follow-up of adverse events

Adverse events that are ongoing after study drug discontinuation for a given patient must be followed until 30 days after study drug discontinuation, or until resolution or stabilization, or until the event is otherwise explained.

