11.13. Follow-up of Patients With an Adverse Event

The Investigator will follow patients with AEs, even if the patient was withdrawn from the study due to the AE, until the adverse event has resolved:

- the patient has returned to baseline state of health,
- the patient is lost to follow-up,
- the event is otherwise explained,
- the Investigator does not expect any further improvement or worsening of the adverse event.

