² ECG will be performed at baseline; 2 hours and 24 hours after the 1st SGT-53 infusion; weekly (2 hours post-infusion) during the first 2 weeks of Cycle 1 and at the EOT visit when the patient goes off study. If these patients receive additional rounds of SGT-53/Temozolomide a 12-lead ECG will only be performed as necessary and the EOT visit when the patient goes off study..

³ Medical History includes review of concomitant medications and adverse events.

⁴ Hematology values include complete white count (CBC) with differential and platelet count.

⁵ PT/PTT and D-dimer for the first two subjects: at baseline/screening; ~20 hours post-infusion (during the 23 hour observation period after the first SGT-53 infusion), and thereafter once a week during Cycle 1, once in two weeks during Cycles 2 and 3; and at the exit visit. When blood chemistries are not being assessed on this same day LDH will also be determined. PT/ PTT and D-dimer for subsequent subjects: at baseline/screening; at Cycle 1, ~20 hours post-infusion 1 (during the 23 observation period); and at the exit visit. When blood chemistries are not being assessed on this same day LDH will also be determined.

⁶ Chemistries include: BUN, Cr, Na*, K*, CO2, Cl, Mg**, Ca**, phosphorus, albumin, alkaline phosphatase, ALT, AST, total and direct bilirubin, total protein, glucose and LDH..

⁷ A limited ECHO will only be performed if needed..

⁸ Tumor size will be assessed by MRI at baseline, every 2 cycles (8 weeks) and/or at the end of cycle 3 to determine if the patient is to continue on study

⁹ Prior to each infusion of SGT-53, subjects will receive the following premedication: dexamethasone (i.v.), a combination of histamine H1 and H2 blockers (i.v.), indocin (p.o.) and acetominophen (p.o.).

¹⁰ Hematology and Full panel chemistries will be completed at each visit only if they were clinically significant at the previous visit.

¹¹ The 30 day and long-term follow-ups will be performed as described in Section 10.3

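### In patients who finish their last planned course on schedule and stop both drugs, no blood count is scheduled at the protocol's own median temozolomide nadirs

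*Combined protocol and SAP*

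**What the plan says.** During therapy, Section 10.2.3 provides: "Patients will return to clinic at least weekly for assessments (until the last week of protocol therapy". The Cycle 3 calendars in 18.1.1 and 18.1.2 put hematology on D1, D8, D15, D22, at EOT and at the 30-day visit. Section 10.2.4 sets the EOT visit: "End of Treatment Evaluations (Day 85, at the end of Cycle 6 if the patient received cycles 4-6"; a CBC is part of it. The next count comes under Section 10.3: "All patients who received treatment with SGT-53 must be followed-up for 30 days after discontinuation of study drug". The calendar adds nothing beyond this: "The 30 day and long-term follow-ups will be performed as described in Section 10.3".

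Four other provisions touch the period after EOT:

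- Section 10.3, removal for toxicity: "If the patient was removed from the Study for toxicity, the patient should be followed with weekly clinic visit and laboratory studies as appropriate".
- Section 11.5: "Adverse events that are ongoing after study drug discontinuation for a given patient must be followed until 30 days after study drug discontinuation", or until the event resolves, stabilizes or is otherwise explained.
- Section 11.13: "The Investigator will follow patients with AEs, even if the patient was withdrawn from the study due to the AE".
- The calendar footnote on repeat laboratory work: "Hematology and Full panel chemistries will be completed at each visit only if they were clinically significant at the previous visit".

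Section 7.1 gives the expected timing of myelosuppression in refractory anaplastic astrocytoma: median nadir 26 days for platelets (range 21-40) and 28 days for neutrophils (range 1-44), with recovery on average within 14 days of the nadir. Section 11.6 plans to evaluate how long grade 3 and 4 hematological events take to recover. Safety of the combination is a secondary objective.

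**The concern.** The weekly counts stop just before the time when the protocol itself expects the lowest values. While treatment continues this does not matter, because the next cycle's visits supply the later counts. After the last course there is no next cycle.

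Two things are at stake for patients who finish on schedule and stop both drugs. First, a grade 3-4 cytopenia after the last course can be missed, or seen only at the 30-day visit without its onset or depth, and this feeds into the Section 11.6 evaluation. Second, a patient with a low count and no symptoms has no scheduled test near the expected nadir.

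The gap may be a by-product of the dosing days. Section 9.7.2 still describes temozolomide on the first five days of later cycles. On that schedule the first Cycle 3 dose would be on Day 57 and EOT would be temozolomide day 29, past both medians. This explanation is an inference; the protocol gives no reason.

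**Working it through.** **Inputs.** Cycle length is 28 days, and Cycle 3 starts on Day 57 (Section 4.6). Temozolomide is given on cycle days 9-13 and the last SGT-53 infusion is on cycle day 18 (Section 5). EOT is Day 85 (10.2.4). Nadir and recovery times are from 7.1.

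**The plan's own figure.** 3 × 28 + 1 = Day 85, as stated for EOT.

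**Last course (Cycle 3).** Temozolomide runs from 57 + 8 = Day 65 to 57 + 12 = Day 69. The last SGT-53 infusion is 57 + 17 = Day 74. With the first dose as day 1, temozolomide day = study day − 64.

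| Scheduled count | Study day | Temozolomide day |
|---|---|---|
| Cycle 3 D15 | 71 | 7 |
| Cycle 3 D22 | 78 | 14 |
| EOT | 85 | 21 |
| 30-day visit, from last temozolomide dose | 69 + 30 = 99 | 35 |
| 30-day visit, from last SGT-53 infusion | 74 + 30 = 104 | 40 |
| 30-day visit, from EOT | 85 + 30 = 115 | 51 |

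The protocol does not say which drug's discontinuation starts the 30 days, so all three readings are shown. The interval after EOT is 99 − 85 = 14, 104 − 85 = 19 or 115 − 85 = 30 days, against 7 days before it.

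**Where the medians fall.** The protocol does not give the day origin for the nadirs. With the first dose as day 1 they are 64 + 26 = Day 90 and 64 + 28 = Day 92. Counted from the last dose they are 69 + 26 = Day 95 and 69 + 28 = Day 97. All four days lie after Day 85 and before Day 99, so inside the gap on every reading.

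**How much of the quoted ranges is unsampled** (first dose = day 1). Platelets, days 21-40: 13 (days 22-34), 18 (22-39) or 19 (22-40) of 20 days. Neutrophils, days 1-44: 13, 18 or 23 (22-44) of 44 days. These are calendar days, not proportions of patients; some nadirs will fall on or near a scheduled count.

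**Recovery.** Nadir plus 14 days is 90 + 14 = Day 104 to 92 + 14 = Day 106. The 30-day visit is 5-7 days before that (Day 99), 0-2 days before (Day 104) or 9-11 days after (Day 115). On the last reading an event can begin and resolve between two counts.

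**Earlier courses.** The Cycle 2 course starts on Day 29 + 8 = 37. Cycle 3 D8 is Day 64, and 64 − 37 + 1 = temozolomide day 28. The same holds for Cycle 1, so earlier courses are covered.

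**Cycle 6.** The calendars stop at Cycle 3. If the same weekly schedule applies, Cycle 6 starts on 5 × 28 + 1 = Day 141, temozolomide on Day 149, and EOT is about Day 169 (temozolomide day 21). The medians are Days 174 and 176.

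**Likely number of events.** Section 7.1 gives grade 3-4 rates of 8% (neutrophils) and 14% (platelets) in newly diagnosed glioblastoma. Applied to 26 patients: 0.08 × 26 = 2.1 and 0.14 × 26 = 3.6 over all courses. Spread evenly over three courses (an assumption), 2.1 / 3 = 0.7 and 3.6 / 3 = 1.2 fall in the last course. From these come off patients who do not complete, those who go on to Cycle 4, and events seen at EOT or the 30-day visit. That leaves about one or fewer of each type.

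**The case against.** The best reply accepts the calendar and disputes the consequence. A nadir is not a grade 3-4 event: in the anaplastic astrocytoma data only 14% (neutrophils) and 20% (platelets) of patients had a nadir that may have delayed the next cycle. Section 7.1 adds that myelosuppression usually came in the first few cycles and was not cumulative. Patients entered having tolerated temozolomide (inclusion criterion 7). Those with grade 3-4 cytopenia that does not resolve within 14 days, or that recurs at the lowest dose, are withdrawn and should then fall under the weekly laboratory follow-up. No temozolomide dosing decision remains after the last course, and weekly counts already blur onset and depth in every cycle.

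Most of this stands, and it is why the size is put at about one event or fewer of each type. Two parts carry less weight. Cycle 3 is itself among the first few cycles, and it is one of only two courses planned at 200 mg/m² in a three-cycle patient. The other follow-up rules also do not fill the gap: weekly laboratory work needs removal for toxicity, Sections 11.5 and 11.13 need an event already detected, the footnote works only at visits that exist, and the two-monthly visits list no CBC.

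A reader might infer that many last-course grade 3-4 events would be lost, or that every patient faces a 30-day gap. The documents support neither. The quoted rates imply few events, 30 days is the longest of three readings, and patients who go on to Cycle 4 are covered until their own last course. The point does not extend to patients who stop mid-cycle, whose EOT can fall on another day, or to those who continue temozolomide alone, who have no calendar.

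**Conclusion.** The point holds for patients who complete Cycle 3, or Cycle 6 if given, on schedule and then stop both drugs. No count is scheduled at either quoted median nadir, under either day origin and all three readings of the 30-day visit. The calendar fact is firm.

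The consequence is modest. The estimate of about one or fewer missed or mis-timed grade 3-4 events of each type rests on rates from newly diagnosed patients and an even spread over three courses. Rates in this pretreated population on the combination could be higher. The nadir days come from anaplastic astrocytoma and have wide ranges, but they are the only ones the protocol gives. PFS6 and the Simon rule are unaffected. What remains is a small patient-safety gap and a weaker Section 11.6 evaluation for the last course, which a cheap change would improve.

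**What to change.** Add to Sections 10.2.4 and 10.3 and to the 18.1 calendars: *For patients who complete their last temozolomide course and start no further temozolomide, one CBC with differential and platelets is done at about temozolomide day 28 of that course, first dose = day 1 (Day 92 after Cycle 3, about Day 176 after Cycle 6). A local draw is allowed. It is repeated weekly while ANC is <1,500/mm³ or platelets are <100,000/mm³.*

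After Cycle 3 this cuts the first interval after EOT to 92 − 85 = 7 days and restores the day-28 count that earlier courses have. It does not close the gap fully. If nadirs are counted from the last dose, the draw comes 95 − 92 = 3 to 97 − 92 = 5 days before the medians, and a normal result leaves 7, 12 or 23 days to the 30-day visit (Day 99, 104 or 115).

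The cost is at most one extra scheduled CBC per patient, in 26 patients or fewer, plus weekly repeats only where counts are low. Dosing, efficacy assessments and sample size do not change.

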10.3.1. Long Term Follow-up

The FDA currently recommends that safety data from participants participating in studies evaluating gene transfer vectors be collected for 15 years (post gene transfer). All participants receiving a dose of SGT-53 will continue to be followed after the completion of all study related procedures to meet the requirements of 15 years post gene transfer follow-up.

All participants upon completion or exit from the study will be presented with written instructions on how to contact the investigator if they experience any serious adverse event that they consider possibly related to study agent or study participation. All participants will be instructed to notify the investigator of a change of address or contact information.

Participants will be contacted on an annual basis by the Principal Investigator and requested to provide information concerning any cancer, neurological, autoimmune, or hematological disorder that occurred or worsened since last contact. The participants will also be requested to provide information concerning any unexpected medical problems including hospitalizations or use of medications. Information will be collected via questionnaire, either by mail or by telephone. The investigator will submit these follow-up data to the sponsor.

The sponsor will submit all information collected during long-term follow-up in annual reports to the FDA. All participants participating in the study will receive an explanation of these procedures at the time of Informed Consent

10.4. Efficacy Assessments

10.4.1. Progression-Free Survival

The percentage of patients who are alive and progression-free clinically and radiologically 6 and 12 months after starting treatment will be evaluated using the Kaplan-Meier method. Progression is defined by any of the following using the RANO criteria:

- a) >25% increase in sum of the products of perpendicular diameters of enhancing lesions compared with the smallest tumor measurement obtained either at baseline (if no decrease) or best response, on stable or increasing doses of corticosteroids*.
- b) Significant increase in T2/FLAIR non-enhancing lesion on stable or increasing doses of corticosteroids compared with baseline scan or best response after initiation of therapy *not caused by co-morbid events (e.g. radiation therapy, demyelination, ischemic injury, infection, seizures, postoperative changes, or other treatment effects)
- c) Any new lesion

- d) Clear clinical deterioration not attributable to other causes apart from the tumor (e.g. seizures, medication adverse effects, complications of therapy, cerebrovascular events, infection, and so on) or changes in corticosteroid dose
- e) Failure to return for evaluation as a result of death or deteriorating condition
- f) Clear progression of non-measurable disease

Note: All measurable and non-measurable lesions must be assessed using the same techniques as at baseline.

*Stable doses of corticosteroids include patients not on corticosteroids.

10.4.2. Tumor response rate:

The percentage of patients with a complete or partial response 6 and 12 months after starting treatment will be evaluated using the RANO criteria:

Complete response (CR). Requires all of the following

- a) complete disappearance of all enhancing measurable and non-measurable disease sustained for at least 4 weeks
- b) no new lesions
- c) stable or improved non-enhancing (T2/FLAIR) lesions
- d) patients must be off corticosteroids (or on physiologic replacement doses only)
- e) stable or improved clinically

Note: Patients with non-measurable disease only cannot have a complete response; the best response possible is stable disease.

Partial response (PR). Requires all of the following:

- a) >50% decrease compared with baseline in the sum of products of perpendicular diameters of all measurable enhancing lesions sustained for at least 4 weeks
- b) No progression of non-measurable disease
- c) No new lesions
- d) Stable or improved non-enhancing (T2/FLAIR) lesions on same or lower dose of corticosteroids compared with baseline scan

- e) The corticosteroid dose at the time of the scan evaluation should be no greater than the dose at the time of baseline scan
- f) Improved or stable clinically

Note: Patients with non-measurable disease only cannot have a partial response; the best response possible is stable disease.

Stable disease (SD). Requires all of the following:

- a) Does not qualify for complete response, partial response, or progression
- b) Stable non-enhancing (T2/FLAIR) lesions on same or lower dose of corticosteroids compared with baseline scan. In the event that the corticosteroid dose was increased for new symptoms and signs without confirmation of disease progression on neuroimaging, and subsequent follow-up imaging shows that this increase in corticosteroids was required because of disease progression, the last scan considered to show stable disease will be the scan obtained when the corticosteroid dose was equivalent to the baseline dose.

